Few studies have examined the effectiveness of an exercise training program coupled with a memory training program. Given the success of exercise programs with healthy older adults and evidence of some positive effects of in MCI patients, it is important to determine if alternative approaches, such as water-based activity, will extend the benefit for those individuals in whom weight-bearing exercise is not possible. The knowledge gained from this proposal will lay the groundwork for a large-scale clinical trial testing hypotheses about the efficacy of nonpharmacological interventions that target cognitive impairment in persons with MCI. The goal of pilot work is to ascertain that the proposed methods are adequate for a large-scale clinical trial in terms of recruitment and retention of appropriate subjects, inclusion and exclusion criteria, appropriateness of treatment condition, and measures.

The aims listed below will be tested in a two-phase single-arm trial conducted at the VA Palo Alto Health Care System (VAPAHCS) that will include: 1) a physical exercise phase and 2) a cognitive training phase. The six-month exercise phase will consist of non-weight bearing water-based physical exercises. After the six-month exercise phase, veterans will complete a two-week cognitive training program. This two-year proposal will include 50 veterans with MCI aged 50 years to 90.

**Specific Aim 1:** To determine the feasibility of a randomized, controlled trial combining physical activity + cognitive training in persons with MCI as shown by good recruitment and retention rates.

**Specific Aim 2:** To evaluate the appropriateness of suggested inclusion and exclusion criteria for the aims of the proposed project.

**Specific Aim 3:** To evaluate appropriateness of the water-based physical exercise + cognitive training (WATER + CT) conditions for study goals.

**Specific Aim 4:** To assess the ability of selected outcome measurement techniques to determine the efficacy of WATER+CT.

**Specific Aim 5:** To examine outcome "moderator" and "mediator" measurement techniques to determine: a) in whom and under what conditions clinically relevant change occurs and b) the mechanisms through which clinically relevant change occurs.

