*Several possibilities exist as to how physical activity impacts cognition. Two primary mechanisms of change that have received increased attention are: 1) improvement in cardiorespiratory fitness with reduction in vascular risk factors (Richardson et al., 2001) and 2) increased expression of brain derived neurotropic factor (BDNF). BDNF induces hippocampal neurogenesis, which influences neural plasticity and results in improved learning and memory (Lista & Sorrentino, 2010). Both vascular risk factors and BDNF are modifiable through physical activity thus both present as potential mechanisms through which physical activity exerts its positive effect on cognition. It is plausible that by improving neural plasticity or reducing vascular risk factors prior to beginning cognitive training, we can augment the effects of a cognitive training program. Put a different, if we are able to improve cognitive mechanisms, such as working memory, PRIOR to cognitive training, persons with MCI may receive greater benefit from the cognitive training program due to improved neural plasticity. Please see the Preliminary Work section for supporting evidence from our Current Work.*

Exercise Trials for Older Adults Show Promise as an Intervention. Clinical trials of physical exercise and its effects on cognition in older adults with and without cognitive decline have noted benefits ranging from significant gains in one-third of the studies of healthy older adults and to significant gains in two-thirds of the studies of cognitively impaired older adults (Colcombe et al., 2003; van Uffelen et al., 2008). There is also some evidence that exercise trials show promise as an intervention to prevent or delay cognitive impairment in persons with MCI (Baker et al., 2010) but this research is plagued by methodological issues including small *n* designs, lack

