Ongoing Study: Exercise Training + Cognitive Training. We have successfully collaborated on the current DOD-funded project, "A Combined Training Program for Veterans with Amnestic Mild Cognitive." This project represents the merging of our interests, namely cognitive training and exercise training, towards a new target problem. At completion in September 2015, this ongoing RCT will compare the effects of a combined aerobic and resistance exercise program + cognitive training (CARE + CT) program to a stretching exercise + cognitive training (SE+ CT) program. Interim results indicate that the intervention is relatively well received by participants, as recruitment and retention rates are positive. To date, fifty-five veterans have been randomized to either the CARE+CT or SE+CT condition. Approximately 8% of those randomized have been lost to follow-up. Reasons for discontinuing study participation were largely due to development of acute illness (i.e., CVA or cancer) or injury (i.e., concussion sustained after fall) that prevented further study participation. There are no group-based differential dropout rates. *The preliminary results of this trial suggest that physical exercise does augment the effect of cognitive training as the CARE+CT group, compared to the SE+CT group, demonstrated clinically significant improvements on measures of learning (CARE+CT group: mean gain score = 13.5, SD=11.21; SE+CT group: mean gain score = 9.5, SD=9.68) and delayed recall (CARE+CT group: mean gain score = 7.25, SD=4.11; SE+CT group: mean gain score = 5.83; SD=2.69).*

Over 1500 veterans have been screened study participation and approximately 15% of those were ineligible due solely to musculoskeletal injuries and illnesses (i.e., impaired gait, osteoporosis, degenerative disc and joint disease) that prevent full engagement in weight-bearing exercises. Given the prevalence of these illnesses and injuries in veterans coupled with the increased risk of cognitive impairment, it is vitally important that we investigate methods to extend the cognitive benefit of physical exercise and cognitive training to all

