Enrollment and Study Implementation. Study staff will explain the study to veterans and, if interested, the consent form and a one page project description will be mailed. Appointments will then be made for three days of evaluation. Day 1: informed consent; cognitive, psychological and functional screening; Day 2: neuropsychological and self-report measures; and Day 3: cardiopulmonary testing and biological measures. When these evaluations are completed, eligible participants will be scheduled for the first exercise session within two weeks. The exercise training portion of intervention is approximately 24 weeks. After completion of the exercise training, participants will be re-assessed with the cardiopulmonary exercise testing, cognitive measures, biological measures, outcome measures, and measures of physical activity. Participants will then begin four weeks of thrice weekly cognitive training classes at VAPAHCS. At completion of the cognitive training, participants will undergo the post-treatment assessment: cardiopulmonary exercise testing, cognitive measures, biological measures, outcome measures, and measures of physical activity. Participants will receive payments of \$50 for each set of assessments completed.

We plan to telephone screen 200 participants, based upon prior work (Myers et al., 2010; Yesavage et al. 2008), half or 100 are expected to proceed to an in-office evaluation (10 per month), half, or approximately 50 enrolled (5 per month). Dropouts will not be replaced as this is a feasibility study and an aim is to evaluate the appropriateness of the inclusion and exclusion criteria.

All in-house exercise sessions and activity surveillance will be supervised by exercise physiologists certified by the American College of Sports Medicine (ACSM). CT will be taught by the PI.

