**Measures**: There are three primary time points (Time 1: Screening/Baseline, Time 2: End of Exercise Training, Time 3: End of CT) at which participants will complete cognitive, psychological, physiological, and biological assessments. Screening measures include measures of episodic memory (Logical Memory I and II from WMS-IV; Wechsler, 2008), mental health (MINI; Sheehan et al., 2002), activities of daily living (Functional Activities Questionnaire (FAQ); Pfeiffer, 1982), a semi-structured interview of cognitive impairment (Clinical Dementia Rating Scale (CDR); Morris, 1993), and assessment of risk factors for vascular dementia (modified Hachinski; Rosen et al., 1980). Measures collected during the cardiopulmonary exercise testing include the VA Prognostic Score, and Veterans Specific Activity Questionnaire (VSAQ; Myers et al., 1994), all of which will be used to estimate risk and assess suitability for exercise training (Gibbons et al., 2002; Morrow et al., 1993). The VSAQ will be used specifically to estimate exercise capacity and thus individualize the intensity during the cardiopulmonary exercise test. Veterans who are not eligible to participate because of cognitive, psychiatric, or medical issues will be referred for further diagnostic work-up or treatment to the Memory Disorders Clinic at VAPAHCs, which provides diagnostic services to older veterans. **Data collected regarding the reasons for exclusion will be analyzed to provide support for the appropriateness of the inclusion and exclusion criteria**. **Feasibility** will be assessed through examination of recruitment and retention rates. **Participant adherence**: Participants will wear heart rate monitors during exercise sessions and pedometers throughout the exercise phase of treatment. They will also log their activities on a 7-day activity recall questionnaire. Data from the pedometers, heart rate monitors and the 7-day activity recall will be collected from participants when they return for the VAPAHCs-based exercise sessions. During CT, participants will have homework and complete quizzes assessing their knowledge of the techniques. They will also complete logs tracking their use of mnemonic techniques. These quizzes and logs of homework completed will serve as measures of participant adherence during the cognitive training portion of the study. The **proposed primary outcome measure** is measure of delayed recall on a 16-item Word-List Task. Equivalent alternate lists of words will be used to counterbalance across time points. The **proposed secondary outcome measure** is recall of a 12-item Name-Face Pair Task. Both the Word-List Task and the Name-Face Pair Task have been used successfully in our prior research and have been shown to be sensitive to the mnemonics taught in the CT (i.e., Method of Loci and Name-Face Mnemonic) (Yesavage et al., 2008). **Cognitive measures** include measures of verbal learning and memory (Rey Auditory-Verbal Learning Test; Lezak, 2004), working memory (Digit Span from WAIS-IV; 2008), processing speed (Symbol Digit Modalities Test; Smith, 1991); attention (Stroop Color and Word Test; Golden 1978), and subjective memory impairment (Multifactorial Memory Questionnaire; Troyer and Rich, 2002). Self-report **measures of physical activity** include the Yale Physical Activity Survey (DiPietro et al., 1993). Finally, **biological measures** will be collected from participants. These include measures of DNA, which will be collected through blood collected at VAPAHCs. We will examine both APOE and BDNF genotypes. The APOE genotyping will be performed according to the restriction isotyping protocol of Hixson and Vernier (1990). BDNF genotyping will also be conducted in-house by [name] staff. Additionally, plasma concentrations of BDNF will be measured using

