### **Database Management and Planned Statistical Analyses**

Data Collection and Database Management. There are three proposed testing time points in this study: prior to randomization (T1), at the end of the exercise program and prior to beginning CT (T2), and at the end of the CT (T3). All identifying information will be removed as data are coded by a unique subject number/identifier. Only the PI and her designee will have access to the identifying information linking subject number to name. All data will be checked for completeness and every effort made to obtain missing data. Data storage will be on computerized password protected databases that are backed up nightly. Additionally, our MIRECC and associated laboratories are familiar with the relevant security and confidentiality issues pertaining to genetic materials and take extra safeguards to protect this information.

Data Analyses. Descriptive analyses of categorical variables will include frequency tables; we will compute measures of central tendency (mean, median, standard deviation, and interquartile range) for those continuous variables. Additionally we will examine the distribution of scores on dependent measures to test assumptions of normality and homogeneity of variance and thus make appropriate transformations when necessary.

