Specific Aim 1: WATER+CT will be feasible as shown by good recruitment and retention rates. Statistical Analyses: To test feasibility of the proposed project, the ratio of enrolled to completed participants will be calculated;  $\geq 80\%$  will be considered good retention. Specific Aim 2: To evaluate the appropriateness of suggested inclusion and exclusion criteria for the aims of the proposed project. Statistical Analyses: We will examine the reported adverse events for participants as well as reasons for screening failures (i.e., those who are consented but excluded from participation prior to randomization). Descriptive analyses of these data will include frequency tables and be used to provide justification for the proposed inclusion and exclusion criteria or to modify them appropriately. Specific Aim 3: To evaluate appropriateness of the WATER+CT for study goals. Statistical Analyses: Appropriateness of treatment conditions will be determined through examination of the participant adherence data. Adherence data will include information from pedometers, heart rate monitors, 7-day activity logs, and cognitive training homework logs. Adequate adherence to exercise prescriptions and CT homework will be defined as completion of  $\geq 80\%$  of assignments as defined by self-report and trainer observation. Specific Aim 4: To assess outcome measurement techniques for participant rate of response in WATER+CT. Statistical Analyses: As this is a single-arm trial, a direct comparison between the WATER + CT condition and a comparative condition is not possible. Participants response rate will be determined by examining the percentage of participants who evidence clinically relevant change after study participation. To determine what a clinically relevant difference in the primary outcome measure (delayed recall of a Word List) would be, we reanalyzed data from our initial clinical trial (Yesavage et al., 2008). Our strategy was to look in that study at the difference in baseline scores between 60 year olds and 70 year olds on the same measure as the proposed work. We found that the difference was 1.7 words. We believe that showing such a difference would be clinically meaningful insofar as it represents a decade of aging's effects on memory. This will be an intent-to-treat analysis, thus all data will be analyzed. Specific Aim 5: To examine outcome "moderator" and "mediator" measurement techniques to determine: a) in whom and under what conditions clinically relevant change occurs and b) the mechanisms through which clinically relevant change occurs. Here we are referring to within subjects effects. Statistical Analyses: Multiple regression modeling will be performed in a preliminary manner to examine individual differences in treatment response depending on baseline (T1) characteristics (age, level of education, APOE and BDNF genotypes). A significant Response Rate X Moderator interaction indicates a differential response rate, e.g., the response rate depends upon age. Such measures are "moderator" variables, i.e., they are used to determine on whom or under what conditions improvement occurs. Additional analyses will be performed to examine the extent to which individual differences in the efficacy of CT treatments depend upon changes in cardiovascular functioning, BDNF plasma levels, and changes in efficiency of working memory (Digit Span) during combined aerobic and resistance exercise training (T1 to T3). These analyses use changes in these two measures as "mediator" variables, i.e., they are used to determine how or why improvement occurs.

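### Aim 5 measures mediator change during exercise from T1 to T3, but exercise ends at T2, so the window includes the cognitive training it is meant to explain

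*Combined protocol and SAP*

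**What the plan says.** Under Database Management and Planned Statistical Analyses, the Specific Aim 5 text names three candidate mediators of CT benefit: cardiovascular functioning, plasma BDNF and Digit Span. It gives the period of change as "changes in efficiency of working memory (Digit Span) during combined aerobic and resistance exercise training (T1 to T3"). The next sentence counts the mediators as two.

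The data collection paragraph of the same section places the second and third assessments "at the end of the exercise program and prior to beginning CT (T2), and at the end of the CT (T3"). The Measures paragraph of Research Design agrees: "Time 2: End of Exercise Training, Time 3: End of CT". Enrollment and Study Implementation gives the order of events: "After completion of the exercise training, participants will be re-assessed with the cardiopulmonary exercise testing, cognitive measures, biological measures", and next "Participants will then begin four weeks of thrice weekly cognitive training classes". Study Procedures, in the human subjects part, repeats that order.

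Background/Significance states the mechanism to be examined. Participants may gain more from CT "if we are able to improve cognitive mechanisms, such as working memory, PRIOR to cognitive training".

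**The concern.** Change during exercise and change from T1 to T3 are different quantities in this design, and the plan equates them. An analyst who follows the bracket computes a mediator that already contains the CT phase. The time order that the hypothesis needs is then lost, because part of the supposed cause is measured during and after the treatment whose effect it should explain.

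Two things could follow. A Digit Span gain made during CT, or a good or bad test day at T3, could produce an association with recall gain when exercise-phase change has none. Alternatively, mediator change after T2 could add noise and hide a real link. Either would pass a misleading mechanism signal to the larger trial that this study is meant to prepare.

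It is also unclear whether the bracket governs Digit Span alone or all three mediators, so the window could be chosen after the data are seen.

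**Working it through.** The plan gives no mediator model, SDs or power for Aim 5, so there is no stated figure to reproduce. The contradiction is settled by the text. The size can only be illustrated.

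**1. Timeline.** T1 to T2 is about 24 weeks of exercise. T2 to T3 is CT, which is four weeks in Research Design and Study Procedures and two weeks in Specific Aims (those passages must be reconciled). No section schedules exercise training during CT.
- CT share of T1 to T3: 4/(24 + 4) = 14%, or 2/(24 + 2) = 8%.
- CT share of T1 to T2: 0%.

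**2. Set-up for the illustration (all inputs assumed).** D1 is true mediator change T1 to T2, D2 is true mediator change T2 to T3, and G is recall gain T2 to T3.
- Standardised scores, independent error SD 0.4 at each visit.
- SD of CT-phase gain 0.7 for recall and 0.5 for the mediator.
- SD of D1 either 0.5 or 0.
- No true link between D1 and G; correlation rho between the true CT-phase gains.

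Var(observed G) = 0.49 + 2(0.16) = 0.81.
Var(observed D1 + D2) = 0.25 + 0.25 + 0.32 = 0.82, or 0.57 if SD(D1) = 0.
Covariance = rho x 0.7 x 0.5 = 0.35 rho.
r = 0.35 rho / sqrt(Var x Var).
Chance of two-sided p < 0.05, with z = atanh(r) x sqrt(n - 3): Phi(z - 1.96) + Phi(-z - 1.96).

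**3. False significance with T1 to T3, n = 50** (first figure SD(D1) = 0.5, second SD(D1) = 0)
- rho 0: 5.0% and 5.0%
- rho 0.1: r = 0.043 and 0.052, giving 6.0% and 6.4%
- rho 0.3: r = 0.129 and 0.155, giving 14.4% and 18.7%
- rho 0.5: r = 0.215 and 0.258, giving 32.1% and 43.9%

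Simulation of 10,000 trials per setting gave 5.0 and 5.3%, 14.4 and 18.9%, and 32.6 and 44.2% at rho 0, 0.3 and 0.5. With T1 to T2 the simulated rate was 4.8-4.9% throughout. At n = 40 (80% of 50), the formula gives 12.4 and 15.7% at rho 0.3, and 26.4 and 36.1% at rho 0.5.

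**4. Shared test-day error, SD 0.3, rho 0, n = 50.** Each change-score variance rises by 2(0.09) = 0.18.
- T1 to T3 mediator: T3 enters both changes with the same sign, so the covariance is +0.09. r = 0.09/sqrt(1.00 x 0.99) = 0.090, or 0.09/sqrt(0.75 x 0.99) = 0.104, giving 9.5% or 11.1%.
- T1 to T2 mediator: T2 enters with opposite signs, so the covariance is -0.09. r = -0.09/sqrt(0.75 x 0.99) = -0.104, or -0.09/sqrt(0.50 x 0.99) = -0.128, giving 11.1% or 14.3%, almost all in the negative direction.
- T1 to T2 adjusted for T1 and T2 recall and the T1 mediator value: 4.9-5.0% in simulation.

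The adjusted model fails elsewhere. If recall and mediator improve together during exercise (correlation 0.5 to 0.8), with no test-day error, it rejects in 7.3-14.1% of null trials, mostly in the positive direction.

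**5. A true link, no test-day error, rho 0, n = 50.** With slope b on D1, the covariance is 0.25b and Var(G) = 0.81 + 0.25b^2.
- b = 0.5: r = 0.125/sqrt(0.57 x 0.8725) = 0.177, power 23% with T1 to T2. With T1 to T3 and SD(D2) = 0.5, r = 0.125/sqrt(0.82 x 0.8725) = 0.148, power about 17%.
- b = 0.8: about 47% against about 35%.
- If the mediator does not change during CT, the two windows have equal power.

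**The case against.** The strongest case against is that this is a small slip in an aim the plan itself calls preliminary, with no documented input that makes the harm large. Most of that stands. The higher error rates need CT-phase gains in Digit Span and recall to correlate at 0.3 to 0.5, which nothing in the documents supports. The rates also take CT efficacy as T2 to T3 recall gain, which the plan never states; Aim 4 scores change after study participation.

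The bracket might be read as the window for CT efficacy, but it follows the mediator phrase and the words about exercise training, so that reading does not fit.

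A reader might infer three stronger points that the documents do not support.
- **That T1 to T3 always weakens a true link.** That was shown only without test-day error. With test-day SD 0.3 and CT-phase mediator SD 0.5, simulated power was 31% (T1 to T3), 6% (T1 to T2 unadjusted) and 21% (T1 to T2 adjusted) at slope 0.5, and 48%, 13% and 39% at slope 0.8. Part of the T1 to T3 figure is positive bias, so this does not vindicate that window.
- **That T1 to T2 removes all bias.** Step 4 of the working shows otherwise.
- **That the exercise wording belongs to another trial.** The ongoing study in Preliminary Work does "compare the effects of a combined aerobic and resistance exercise program + cognitive training (CARE + CT) program", and Specific Aims says of this trial "The six-month exercise phase will consist of non-weight bearing water-based physical exercises". But the WATER and Study Procedures paragraphs include both resistance and aerobic work in the pool, so the phrase can describe this trial. Carried-over text is possible but not shown, and that wording needs no correction.

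**Conclusion.** The window is wrong as written. It contradicts the time points given in several other places, no section corrects it, and it defeats the stated hypothesis of improvement before CT. That conclusion rests on the text alone and is firm.

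The size is not firm. At n = 50, false significance runs from no inflation to 33-44%, depending on a correlation the documents do not give. It would be too strong to say that Aim 5 will produce false mechanisms. What can be said is that its mediator result, computed as written, could not be read as change preceding CT benefit.

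The consequence stays within the mediator part of Aim 5. No feasibility criterion and no sample size depends on it. The correction should be made because the error is certain and the cost is small.

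**What to change.** In the Aim 5 analysis text:
- Change the mediator window from T1 to T3 to T1 to T2, and state that it applies to cardiovascular functioning, plasma BDNF and Digit Span alike.
- Define the CT outcome as the T2 to T3 change in delayed recall on the Word-List Task.
- Correct the mediator count from two to three.
- Because both changes use the T2 visit, report beside the unadjusted estimate a sensitivity model adjusted for T1 and T2 recall and the T1 mediator value. State both limits: shared test-day error pulls the unadjusted association downward, and joint improvement of recall and mediator during exercise can push the adjusted one upward.
- Report estimates with 95% CIs as exploratory. Do not add a rule that both models must agree. With test-day SD 0.3, requiring both to be significant and positive found a true link in only 4.4% (slope 0.5) or 12.6% (slope 0.8) of simulated trials.
- State that, without a control arm, the T1 to T2 window restores time order but does not attribute the mediator change to exercise.

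The cost is a wording change and one extra model per mediator. No new data are needed, since cardiopulmonary, cognitive, biological and outcome measures are already scheduled at T2.

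### Aim 5 reads mechanism from the correlation of mediator change with training gain, which does not show whether the mediator moved at all

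*Combined protocol and SAP*

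**What the plan says.** The mechanism is set out in Background/Significance of the combined protocol and SAP. The authors put it forward as a possibility: "by improving neural plasticity or reducing vascular risk factors prior to beginning cognitive training, we can augment the effects of a cognitive training program". This is a chain of two links: exercise changes the mediator before CT, and the changed mediator raises the benefit from CT.

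The analysis is in Database Management and Planned Statistical Analyses, Specific Aim 5. It examines how far "individual differences in the efficacy of CT treatments depend upon changes in cardiovascular functioning, BDNF plasma levels, and changes in efficiency of working memory", the last measured by Digit Span. The change is taken from T1 to T3. The changes are then labelled mediators, "i.e., they are used to determine how or why improvement occurs". No model, test or indirect-effect estimate is named. Three measures are listed, although the next sentence speaks of two.

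The same section plans means, medians, SDs and interquartile ranges for continuous variables in general. It plans no estimate or test of mean mediator change. Under Specific Aim 4 it acknowledges the design: "As this is a single-arm trial, a direct comparison between the WATER + CT condition and a comparative condition is not possible".

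**The concern.** The claim needs both links, but the analysis looks only at the second, and only through differences between people. Whether people whose mediator changed more also gained more from CT is a different question from whether exercise changed the mediator. The two can part company in either direction:

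- A measure that did not move on average can still correlate with CT gain if something else drives both. Digit Span is the clearest case. It belongs to the same assessment sets as word recall, so effort, fatigue or illness at a visit can shift both scores together.
- A measure that exercise raised by nearly the same amount in everyone may carry the whole benefit, yet has almost no between-person spread to correlate with anything.

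The pilot is meant to prepare a larger trial. At stake is which mechanisms that trial pursues and which it drops.

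**Working it through.** The plan states no figure for the mediator analysis, so there is none to reproduce. The checks below use its own quantities where they exist and labelled assumptions elsewhere.

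**Inputs from the document**
- Enrolment 50 (Sample size). Loss of about 8% in the group's ongoing exercise trial (Preliminary Work): 50 × 0.92 = 46.
- SD of word-list recall gain 4.2 (Preliminary Work, placebo + CT group of the earlier CT trial).
- Clinically relevant difference 1.7 words (Specific Aim 4).

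**Assumptions**
- Two-sided 5% test of zero slope.
- Same-visit error correlation ρ between Digit Span and word recall of 0 to 0.4.
- CT efficacy taken as T2-T3 gain, because CT runs only from T2 to T3.

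**Step 1: the slope ignores the mean.** Adding a constant to everyone's mediator change leaves its covariance with gain unchanged. In simulation (n = 50, correlation of changes set at 0.4 with no causal path), the rejection rate stays at 83-84% as the mean change goes from 0 to 2 SD.

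**Step 2: a true mediator that moves nearly alike in everyone.** Let mediator change have mean 1 and SD s, and let gain rise by 1.7 words per unit, with total SD 4.2. The correlation is r = 1.7s/4.2. Approximate power is Φ(m − 1.96) + Φ(−m − 1.96), with m = atanh(r) × √43.

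| s (SD ÷ mean) | r | Power |
|---|---|---|
| 0 | 0 | 5% |
| 0.25 | 0.101 | 10% |
| 0.5 | 0.202 | 27% |
| 1.0 | 0.405 | 80% (81% simulated) |

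In every row a one-sample test detects the mean change with about 100% power. Even at s = 1.0 its expected t is about √46 = 6.8.

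**Step 3: false naming of Digit Span through shared-visit error.** Suppose exercise has no effect on the mediator, the mediator has none on recall, and each score has independent errors across visits. Mediator change T1-T3 and gain T2-T3 share only the T3 visit. Their covariance is ρσ₁σ₂, where σ₁ and σ₂ are the error SDs, and their variances are 2σ₁² and 2σ₂². Hence r = ρ/2.

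| ρ (assumed) | r | Rejection, n = 46 |
|---|---|---|
| 0 | 0 | 5% |
| 0.1 | 0.05 | 6% |
| 0.2 | 0.10 | 10% |
| 0.3 | 0.15 | 17% |
| 0.4 | 0.20 | 27% |

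Moving the mediator window to T1-T2 does not remove this. The shared visit becomes T2, which enters the two differences with opposite signs, so r = −ρ/2. The rejection rates are the same, but the association is negative.

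**Step 4: the adjusted model.** Regress T3 recall on T1-T2 mediator change, T1 recall and T2 recall (simulated, n = 46, trait variance twice the error variance). Rejection under the null is about 5% at ρ = 0.2 to 0.4 if true recall does not change differently between people during exercise. If it does, with variance equal to the error variance, rejection reaches about 9% at ρ = 0.4. With twice the error variance it is about 12%. The excess is mostly negative in sign.

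**The case against.** The strongest reply is that this is an exploratory aim in a feasibility study. Aim 5 concerns measurement techniques, and feasibility is judged on recruitment and retention, so no go/no-go decision depends on it. The planned descriptives would also let a reader see roughly whether a measure moved. This limits the consequence and stands. It does not rescue the claim: the word preliminary is attached to the moderator regression, while the mediator sentence says the analysis will determine how improvement arises.

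Three further points stand as limits:

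- The plan names no mediator model. The null of zero association is implied by its wording and is not stated.
- False naming above 5% needs a shared cause. No document gives a same-visit correlation, and the argument is made for Digit Span only. At baseline, cardiopulmonary and biological measures are taken on a different day from the neuropsychological tests.
- A regression on between-person change, however adjusted, still cannot see a uniform mediator. Nor can a single arm attribute mean change to exercise, as opposed to time or retesting.

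A reader might infer much higher false-naming rates, because pairing T1-T3 mediator change with T1-T3 recall gain gives about 27%, 54% and 81% at ρ = 0.2, 0.3 and 0.4. The document does not support that as the planned analysis. It speaks of the efficacy of CT, which follows the exercise phase, so T2-T3 gain is the natural outcome.

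**Conclusion.** The concern holds for the inference drawn. The planned association cannot support a statement of mechanism, because it gives the same answer whether or not the mediator moved on average, and the first link in Background/Significance is tested nowhere.

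The miss is close to complete only when mediator change is nearly uniform. It fades as the spread grows, from about 5% power to about 81% when the SD equals the mean. These figures assume 46 completers, full mediation of 1.7 words and a gain SD of 4.2. The false-naming rates for Digit Span of about 10%, 17% and 27% rest on assumed correlations and return to 5% at zero.

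It would go too far to infer that any unmoved measure is likely to be named a mediator, or that the feasibility conclusions are affected. The document supports neither.

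**What to change.** Amend the mediator part of Specific Aim 5 in three ways.

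1. Report the mean T1-T2 change with a 95% CI for cardiovascular functioning, plasma BDNF and Digit Span. Call a measure a candidate mediator only if it moved in the expected direction. State that one arm cannot separate exercise from time or retest effects.
2. As an exploratory association, regress T3 word-list recall on T1-T2 mediator change, adjusting for T1 and T2 recall. State that this reduces shared-visit bias without fully removing it, with the error rates in Step 4. State also that it cannot detect a mediator that moves alike in everyone, so a null slope is not evidence against a measure that moved.
3. Replace the claim "i.e., they are used to determine how or why improvement occurs" with the aim of identifying candidate mediators for the randomised trial.

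All the variables are already scheduled at T1, T2 and T3, so only the analysis wording changes. The cost is one more covariate in a small sample and a more modest claim.
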